## Statistical Analysis Plan

### ***6.1.4.11 Oxygen Use and Related Duration***

Any Oxygen given alone for the normal care of preterm neonates during the study conduct will be documented with:

- Was the subject given Oxygen alone? (Y/N), if answered yes with:
  - Start/End Date and Time.

In addition, all the cases of “Low Flow Nasal Cannula” as reported in the ventilatory parameters pages will be summarized under Oxygen use.

Duration of oxygen use will be calculated as sum of oxygen use/LFNC end date/time minus oxygen/LFNC use started date/time.

To account for missing time in date/time when deriving duration variables, the following approaches will be used:

- Time points with unknown start and/or end times (but where the date is known) will be imputed with a time of 00:00 h or treatment administration time (1st treatment Day 1 only) for the tabulations but will be shown as NK:NK in the listings (where NK = Not Known).

### ***6.1.4.12 Normal breathing (i.e. at room air) patients within 24 hours***

Percentage of patients with at least one reading of FiO2 equal to 0.21 (i.e. at room air) within 24 hours from first intake will be taken as estimation of normal breathing.

Additionally the median duration time to reach FiO2 equal to 0.21 (normal breathing) will be determined.

### ***6.1.4.13 Alveolar–Arterial Gradient***

The alveolar–arterial gradient (A-aO2) is used in determining the source of hypoxemia is derived on the eCRF as difference of alveolar PO2 (PaO2) and arterial PO2.

Values in the first 48 hours after the first surfactant intake (i.e., at 3, 6, 12, 18, 24 hours and on day 2) will be collected, given the challenges to placing arterial catheters in pre-term neonates.

## Statistical Analysis Plan

### **6.1.4.14 Oxygenation Index**

The Oxygenation Index (OI) is a calculation used in intensive care medicine to measure the fraction of inspired oxygen ( $\text{FiO}_2$ ) and its usage within the body according to the following formula (lower oxygenation index is better):

$$\text{OI} = \text{FiO}_2 * \text{MAP} / \text{PaO}_2.$$

Values in the first 48 hours after the first surfactant intake (i.e., at 3, 6, 12, 18, 24 hours and on day 2) will be collected.

## **6.2 Analysis Populations**

### **6.2.1 Safety Population**

The safety population consists of all randomized patients who took at least one dose of study medication.

The safety population (SAF) will be used in the analysis of all safety variables.

In case of deviation between as-randomized treatment and treatment actually received, the treatment actually received will be used in the safety analyses (i.e. an “as-treated” analysis will be performed).

### **6.2.2 Intention-to-Treat Population**

The Intention-to-Treat population (ITT) consists of all randomized patients who received at least one dose of study medication and with at least one available evaluation of efficacy after the baseline.

The efficacy analyses will be performed based on the ITT population.

### **6.2.3 Per Protocol Population**

Considering the exploratory nature of the study, no Per Protocol (PP) analysis is planned. Hence, the need to repeat efficacy analysis on a PP population for specific efficacy parameters has been discussed during the BDRM before database lock based on the amount and kind of major protocol violations.

## Statistical Analysis Plan

The PP Population will then consist of subjects in the ITT population with no major protocol deviations. FiO2 and SpO2/FiO2 analyses will be repeated in the PP population.

### 6.3 Statistical Analysis Methods

#### 6.3.1 Listings and Descriptive Statistics

All original and derived parameters as well as population characteristics will be listed and described using summary statistics. Frequency counts (number of neonates [n] and percentages) will be made for each qualitative variable. General descriptive statistics for numeric variables will include the n (number of observed values), the mean, the standard deviation, the median, the minimum, and the maximum values. For categorical variables, the number and percent of subjects with a specific level of the variable will be presented (if not stated otherwise).

All listings will include unscheduled measurements, i.e. all measured values will be listed. Listings are to be sorted by patient number and then by visit/week/day/timepoint (where applicable).

- All listings will be presented for the randomized population. Screened neonates will be used for disposition listing.
- Randomized treatment and actual treatment will be displayed in ‘Listing 16.1.7 – Randomization Schedule’ and misallocations, if any, will be identified with a flag (§). The actual treatment will be presented in all safety listings, while the randomized treatment will be presented in the efficacy listings.
- In case of values excluded from the analysis, specific flags will be presented.

All descriptive statistics will be presented by treatment.

#### 6.3.2 Statistical Significance Level

All statistical tests will be two-sided and will be performed at the 5% level of significance, unless otherwise stated.

## Statistical Analysis Plan

### 6.3.3 Software

All statistical analyses will be performed using Statistical Analysis Software (SAS®) Version 9.2 or later.

### 6.3.4 Missing Data

Generally there will be no imputation of missing data. Hence critical missing data, if any, will be discussed during the BDRM before database lock. Decisions will be fully documented in the BDRM Report.

### 6.3.5 Interim Analysis

Not applicable.

### 6.3.6 Protocol Deviations

Protocol deviations detected during the study will be collected in a log file list and discussed within [REDACTED] (physician, Data Manager, Biostatistician, PK Scientist/Analyst and Medical Writer). The Sponsor will evaluate the protocol deviations at the BDRM before database lock in order to estimate their influence (major, minor) on study results and to decide whether these deviations may warrant exclusion of a subject from the statistical analyses. Major protocol violations will be listed and summarized by treatment.

### 6.3.7 Patients disposition

Reason for screening failures will be presented with a breakdown of the reasons for discontinuation. Disposition of patients and reason for discontinuations will be presented for the randomized patients population by treatment and overall.

## Statistical Analysis Plan

### 6.3.8 Demographic Data

All demographic data will be presented using the ITT and safety population. Data listings and summary tables will be provided.

### 6.3.9 Mother and Neonatal Concomitant Medication

Any concomitant medication given for the normal care of preterm neonates or used by the neonates' mother during the study will be listed and displayed in a frequency table.

Tables will be presented by Anatomical Main Group (1st level of ATC), Therapeutic Subgroup (2nd level of ATC), Chemical Subgroup (4th level of ATC) and preferred drug name, alphabetically sorted. Code and decode will be displayed as follow:

- R, Respiratory System
  - R03, Drugs for Obstructive Airway Diseases
    - R03CC, Selective Beta-2-Adrenoreceptor Agonists
      - Salbutamol.

In the summaries, subjects experiencing more than one medication classified in the same category (previous medications, concomitant medications) within the same anatomical main group, therapeutic subgroups, chemical subgroup and preferred name will be counted only once.

### 6.3.10 Exposure to the Investigational Medicinal Product

Drug dosing (both initial and re-dosing) information (dosing date/time, volume administered, calculated dose administered), if available, will be presented in a listing (Appendix 16.2.5).

First and cumulative dose as well as total dose administered (mg/kg) will be summarized by treatment. Number and percentage of neonates receiving additional study drug doses will be summarized by treatment, overall and by number of additional doses (1 or 2).

Time since birth to first dose (h) and to each of the additional doses (h) will be summarized by treatment.

## Statistical Analysis Plan

### 6.3.11 Safety Analysis

The analysis of the safety variables will be based on the safety population.

#### 6.3.11.1 Adverse Events

An overall summary of number and percentage of subjects with at least one treatment-emergent AEs, SAEs, ADRs, serious ADRs and AEs leading to death will be presented by treatment. The number of events will be also displayed.

The number and percentage of patients with at least one AE and the number of AEs will be presented by treatment for treatment-emergent AEs, SAEs, ADRs, and AEs leading to death. The summary results will be presented in alphabetic order for the SOC. Within each SOC, the PTs will be presented sorted by decreasing overall frequency (not explicitly displayed).

The following listings will be produced:

- Pre-treatment AEs;
- TEAEs
- ADRs;
- SAEs;
- TEAEs leading to death.

#### 6.3.11.2 Clinical Safety Laboratory Tests (hematology, biochemistry)

Laboratory values (hematology, biochemistry) will be listed by neonates and study time point.

All values outside the clinical reference ranges, if available, will be flagged in the data listings. The abnormal values will be flagged with 'L' for values below the lower limit of the clinical reference range and 'H' for values above the upper limit of the clinical reference range and included in the listings. Clinical significance (NCS or CS), if available, will be listed as well.

## Statistical Analysis Plan

### **6.3.11.3 Vital Signs**

Vital signs data (SBP, DBP, HR, SpO2 during administration) taken on Day -1 will be listed by patient.

Descriptive statistics (n, mean, SD, median, minimum, maximum) for absolute and change from baseline values will be presented by treatment at each time point. SpO2 during administration will be summarized as well.

Time curve of the mean change from baseline in the first week of life will be presented by treatment group.

### **6.3.11.4 Immunogenicity data**

The levels of antibodies in serum will be listed.

‘Not reliable’ immunogenicity values as defined during Blind Data Review meeting will be flagged in the listing.

## **6.3.12 Efficacy Variables**

The efficacy analysis will be based on the ITT population.

The efficacy parameters will be listed by treatment and time point and will include both absolute values and changes from baseline, where applicable.

The baseline for each of these parameters will be the last pre-dose measurement taken on Day -1 (including unscheduled measurements, if available). If no assessment exists before treatment but a measurement is taken exactly at the same time of treatment, this will be used as baseline measurement and mentioned for corresponding outputs. The latest won’t apply to SpO2 since value collected at time 0 is not part of efficacy assessment (See Section 9 of CSP). If measurements at date of treatment have no time information included, it is assumed as taken before treatment time since recorded under screening assessment.

Descriptive statistics of the absolute values and changes from baseline will also be presented.

## Statistical Analysis Plan

Post-treatment unscheduled assessment won't be used in the analysis unless original assessment is not available.

### **6.3.12.1 Statistical Analysis**

#### **6.3.12.1.1 SpO2/FiO2 Ratio**

SpO2/FiO2 will be analyzed using a linear mixed model for repeated measures (MMRM) including treatment, time point, treatment by time point interaction, investigational site and gestational age group as fixed effects and pre-dose ratio as covariate. The adjusted means in each treatment group, the adjusted mean difference between treatments and their 95% confidence intervals (CIs) at each time point and averaged over the first 24 hours will be estimated by the model. The following SAS code will be used:

```
Proc Mixed data= ... (WHERE=(time LE 24));
Class treatment time site agegrp subject;
Model var=treatment time treatment*time site agegrp baseline baseline*time / ddfm=kr;
REPEATED time / subject=subject type=UN;
Lsmeans treatment*time / PDIFF CL alpha=0.05;
Lsmeans treatment / PDIFF CL alpha=0.05; * for overall;
Estimate 'CHF5633 - Curosurf: 30 min' treatment 1 -1 treatment*time 1 0 0 0 0 0 0 -1 0 0 0 0 0 0 /CL alpha=0.05;
Estimate 'CHF5633 - Curosurf: 1 hr' treatment 1 -1 treatment*time 0 1 0 0 0 0 0 0 -1 0 0 0 0 0 0 /CL alpha=0.05;
Estimate 'CHF5633 - Curosurf: 3 hrs' treatment 1 -1 treatment*time 0 0 1 0 0 0 0 0 0 -1 0 0 0 0 0 /CL alpha=0.05;;
Estimate 'CHF5633 - Curosurf: 6 hrs' treatment 1 -1 treatment*time 0 0 0 1 0 0 0 0 0 0 -1 0 0 0 0 /CL alpha=0.05;
Estimate 'CHF5633 - Curosurf: 12 hrs' treatment 1 -1 treatment*time 0 0 0 0 1 0 0 0 0 0 0 -1 0 0 /CL alpha=0.05;
Estimate 'CHF5633 - Curosurf: 18 hrs' treatment 1 -1 treatment*time 0 0 0 0 0 1 0 0 0 0 0 0 -1 0 /CL alpha=0.05;
Estimate 'CHF5633 - Curosurf: 24 hrs' treatment 1 -1 treatment*time 0 0 0 0 0 0 1 0 0 0 0 0 0 -1 /CL alpha=0.05;
Estimate 'CHF5633 - Curosurf: Overall' treatment 1 -1 / CL alpha=0.05;
ods output estimates=estim lsmeans=ls_means;
QUIT;
/* baseline=pre dose value, agegrp=gestational age group, time in hours */
Time profile plot of mean SpO2/FiO2 in the first 24 hours post treatment will be presented
by treatment group.
```

SpO2/FiO2 will be compared between treatments at the remaining post-treatment time points (i.e., Days 2, 3, 5, 7, 28±2 PNA, at discharge home and at 36 weeks PMA) using mixed model including

Chiesi

Final 1.0

CCD-5633AA1-02

18/July/2018

---

TP-EP.BS-WW-001-05

Effective date: 29 Jul 15

Related to: SOP-EP.BS-WW-002

Page 30 of 46

## Statistical Analysis Plan

treatment, investigational site and gestational age group as fixed effects and pre-dose ratio as covariate. These results will be displayed in a separate table.

SpO2/FiO2 summary and analyses will be repeated also in the PP population.

According to the protocol, if the discharge home coincides with 36-wks PMA assessment, data are entered once in the eCRF at 36-wks PMA. In this case, data of 36-wks PMA should be used also for discharge summary and analysis.

The following SAS code will be used:

```
Proc Mixed data= ...;
  Class treatment site agegrp;
  Model var=treatment site agegrp baseline / ddfm=kr;
  Lsmeans treatment / CL alpha=0.05;
  Estimate 'CHF5633 - Curosurf' treatment 1 -1/
    DIFF cl alpha=0.05;
  ods output estimates=estim
    lsmeans=ls_means;
  BY day;
  QUIT;
/* baseline=pre dose value, agegrp=gestational age group */
```

SpO2/FiO2 will be analyzed by subgroups based on ventilator support used.

### 6.3.12.1.2 FiO2

FiO2 will be analyzed at each time point and averaged over the first 24 hours post dose using the same model used for the SpO2/FiO2. Pre-dose FiO2 will be used as covariate.

Time profile plot of mean FiO2 in the first 24 hours after treatment will be presented by treatment group.

FiO2 will be compared between treatments at additional post-treatment time points (i.e., Days 2, 3, 5, 7, 28±2 PNA, at discharge home and at 36 weeks PMA) using linear mixed model including, treatment, investigational site and gestational age group as fixed effects and pre-dose FiO2 as covariate. Same SAS code displayed in the SpO2/FiO2 analysis will be used.

Chiesi

Final 1.0

CCD-5633AA1-02

18/July/2018

---

TP-EP.BS-WW-001-05

Effective date: 29 Jul 15

Related to: SOP-EP.BS-WW-002

Page 31 of 46

## Statistical Analysis Plan

FiO2 summary and analyses will be repeated also in the PP population.

According to the protocol, if the discharge home coincides with 36-wks PMA assessment, data are entered once in the eCRF at 36-wks PMA. In this case, data of 36-wks PMA should be used also for discharge summary and analysis.

### 6.3.12.1.3 RSS

RSS, calculated from ventilator settings as MAP x FiO2, will be analyzed at each time point and averaged over the first 24 hours post study drug intake using the same model used for the SpO2/FiO2.

Time profile plot of mean RSS in the first 24 hours after treatment will be presented by treatment group.

RSS at Day 2 will be analyzed using linear mixed model including, treatment, investigational site and gestational age group as fixed effects.

Same SAS code displayed in the SpO2/FiO2 analysis will be used.

According to the protocol, if the discharge home coincides with 36-wks PMA assessment, data are entered once in the eCRF at 36-wks PMA. In this case, data of 36-wks PMA should be used also for discharge summary and analysis.

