| Sample size calculation | According to the exploratory nature of this study, no formal sample size calculation was performed. A maximum number of sixty-three randomized neonates per treatment group (126 in total) is deemed sufficient to describe the efficacy and safety of CHF5633 compared to Poractant Alfa. |
| Statistical methods | 
Efficacy variables
 
• $\text{SpO}_2/\text{FiO}_2$ will be analyzed using a linear mixed model for repeated measures (MMRM) including treatment, time point, treatment by time point interaction, investigational site and gestational age group as fixed effects and pre-dose ratio as covariate. The adjusted means in each treatment group, the adjusted mean difference between treatments and their 95% confidence intervals (CIs) at each time point and averaged over the first 24 hours will be estimated by the model.• $\text{SpO}_2/\text{FiO}_2$ will be compared between treatments at the remaining post-treatment time points (i.e., Days 2, 3, 5, 7, 28 ± 2 PNA, at discharge home and at 36 weeks PMA) using mixed model including treatment, investigational site and gestational age group as fixed effects and pre-dose ratio as covariate.• $\text{SpO}_2/\text{FiO}_2$ will be analyzed by subgroups based on ventilator support used.• FIO_2 will be analyzed at each time point and averaged over the first 24 hours post dose using the same model used for the $\text{SpO}_2/\text{FiO}_2$. Pre-dose FIO_2 will be used as covariate.• FiO_2 will be compared between treatments at additional post-treatment time points (i.e., Days 2, 3, 5, 7, 28 ± 2 PNA, at discharge home and at 36 weeks PMA) using linear mixed model including, treatment, investigational site and gestational age group as fixed effects and pre-dose FIO_2 as covariate.• RSS will be analyzed at each time point and averaged over the first 24 hours post study drug intake using the same model used for the $\text{SpO}_2/\text{FiO}_2$.• RSS at day 2 will be analyzed using linear mixed model including, treatment, investigational site and gestational age group as fixed effects.• OSI will be analyzed at each time point and averaged over the first 24 hours post study drug intake using the same model used for the $\text{SpO}_2/\text{FiO}_2$. |

OSI at day 2 will be analyzed using linear mixed model including, treatment, investigational site and gestational age group as fixed effects.

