- RSS will be compared between treatments at day 2 using linear mixed model including, treatment, investigational site and gestational age group as fixed effects.

Oxygen saturation index

- OSI, will be calculated as MAP x FiO₂ x 100/ SpO₂ and analyzed at each time point and averaged over the first 24 hours post study drug intake using the same model used for the SpO₂/FiO₂.

Time profile plot of mean OSI in the first 24 hours after treatment will be presented by treatment group.

- OSI will be compared between treatments at day 2 using linear mixed model including, treatment, investigational site and gestational age group as fixed effects.

SpO₂

- SpO₂ values as well as changes from baseline will be summarized at any post-treatment time point by treatment group by means of descriptive statistics.

MAP, PIP, PEEP

- MAP, PIP, PEEP values as well as changes from baseline will be summarized at any post-treatment time point by treatment group by means of descriptive statistics.

Duration of ventilation/oxygen use

- The median duration time (days) of invasive mechanical ventilation, oxygenation, non-invasive ventilation will be compared between treatment groups by using the Mann-Whitney U-test.

Mortality and BPD

- Mortality/BPD rate at 36-week PMA will be compared by treatment by means of Cochran-Mantel-Haenszel (CMH), adjusting for stratification factors (i.e. GA group and investigational site). Relative Risk (RR) and related 95% confidence interval will be provided.
- The incidence of BPD at 36-week PMA will be compared by treatment as for Mortality/BPD rate.
- The mortality rate at 36-week PMA and at Day 28 will be compared by treatment as for Mortality/BPD rate.
- RDS-associated mortality rate through 14 days of age will be compared by treatment as for Mortality/BPD rate.

Rescue surfactant use

The percentage of patients requiring at least one rescue surfactant dose will be compared by treatment group by means of a Fisher's exact test at 5% significance interval. Odds ratio (OR) and related exact 95% CI will be also provided. Patients with pulmonary haemorrhage will be excluded from this summary.

Biomarkers of inflammation

Mean values of biomarkers of inflammation (i.e., CXCL8, IL1 β , IL6, TNF- α , MPO) in the tracheal aspirates as well as change from baseline to 24 and day 2 (48 hours) will be summarized by treatment by means of descriptive statistics.

Alveolar-arterial gradient and Oxygenation Index

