### 6.3.12.1.4 OSI

OSI, will be calculated as MAP x FiO2 x 100/SpO2, will be analyzed at each time point and averaged over the first 24 hours post study drug intake using the same model used for the SpO2/FiO2.

Same SAS code displayed in the SpO2/FiO2 analysis will be used.

Time profile plot of mean OSI in the first 24 hours after treatment will be presented by treatment group. OSI at Day 2 will be analyzed using linear mixed model including, treatment, investigational site and gestational age group as fixed effects.

Same SAS code displayed in the SpO2/FiO2 analysis will be used.

Chiesi

Final 1.0

CCD-5633AA1-02

18/July/2018

---

TP-EP.BS-WW-001-05

Effective date: 29 Jul 15

Related to: SOP-EP.BS-WW-002

Page 32 of 46

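### The Day 2 RSS and OSI model text omits the pre-dose value that the cited SAS code includes, so text and code give two different models

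*SAP*

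**What the plan says.** **Day 2 text.** SAP 6.3.12.1.3: "RSS at Day 2 will be analyzed using linear mixed model including, treatment, investigational site and gestational age group as fixed effects". SAP 6.3.12.1.4: "OSI at Day 2 will be analyzed using linear mixed model including, treatment, investigational site and gestational age group as fixed effects". The protocol outline (statistical methods) has "RSS at day 2 will be analyzed using linear mixed model including, treatment, investigational site and gestational age group as fixed effects", and protocol 12.3.4 has "RSS will be compared between treatments at day 2 using linear mixed model including, treatment, investigational site and gestational age group as fixed effects". Both protocol places carry a matching OSI sentence. None of them names a pre-dose value.

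**Code cited.** Both SAP sections then refer to the code shown for SpO2/FiO2; the sentence begins "Same SAS code displayed in the SpO". SAP 6.3.12.1.1 shows two blocks. The by-day block, which is the one that fits Day 2, has "Model var=treatment site agegrp baseline / ddfm=kr". The first-24-hours block has "Model var=treatment time treatment*time site agegrp baseline baseline*time / ddfm=kr". A comment under each block defines baseline as the pre-dose value.

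**Contrast.** For FiO2 at its later time points, the text of SAP 6.3.12.1.2 does name the covariate: "gestational age group as fixed effects and pre-dose FiO" (the quote stops at the subscript).

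**Data available.** Protocol 7.1.1 collects RSS and OSI before dosing, and SAP 6.3.12 defines baseline as the last pre-dose measurement.

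**MAP.** SAP 6.1.4.4 and 6.1.4.5 multiply by MAP at every time point to Day 2. Protocol 7.1.2 and 7.1.3 foresee oxygen alone, without ventilator support, in that window. SAP 6.3.4 generally imputes nothing and sends critical missing data to the blind data review.

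**The concern.** A programmer who follows the Day 2 sentence fits an unadjusted model. One who runs the cited code adjusts for the pre-dose value. Both models can be fitted from the data collected, so the SAP does not fix a single answer.

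The pre-dose value matters for two reasons. It is likely to predict Day 2 severity, so leaving it out costs precision. The minimization balances only site and gestational age group (protocol 6.5), so a chance imbalance in pre-dose RSS would pass into an unadjusted estimate.

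The second gap concerns babies off positive pressure. They have no obvious MAP, and the plan does not say whether RSS and OSI are then blank, zero or something else. Such babies have plausibly improved. RSS and OSI are the only outcomes containing airway pressure that are modelled between arms: MAP, PIP, PEEP and the Oxygenation Index are only summarised (SAP 6.3.12.1.6 and 6.3.12.1.13).

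**Working it through.** The plan states no figure for these models and no formal sample size calculation, so there is nothing to reproduce. The check is a comparison of text with code, then the cost of choosing one over the other.

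**1. Terms in the Day 2 model**

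| Source | Treatment | Site | GA group | Pre-dose value |
|---|---|---|---|---|
| Protocol outline and 12.3.4, RSS and OSI | yes | yes | yes | no |
| SAP 6.3.12.1.3 and 6.3.12.1.4, text | yes | yes | yes | no |
| SAP 6.3.12.1.1, by-day code | yes | yes | yes | yes |
| SAP 6.3.12.1.2, FiO2 text, later time points | yes | yes | yes | yes |

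The 24-hour code also contains baseline, so the conflict remains whichever block is meant. The FiO2 text shows that omitting the covariate is not the SAP's usual shorthand.

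**2. Cost of following the text**

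Inputs: 126 babies (protocol 12.1) and about 20 sites (protocol outline). The correlation rho between pre-dose and Day 2 RSS, given treatment, site and GA group, is assumed, because the documents give none.

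The unadjusted model uses 1 (intercept) + 1 (treatment) + 19 (sites) + 1 (GA group) = 22 parameters. The adjusted model uses 23.

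SE(adjusted)/SE(unadjusted) = sqrt[(1 - rho²) × (126 - 22)/(126 - 23)] = sqrt[(1 - rho²) × 104/103]

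| rho (assumed) | SE ratio | SE excess without covariate |
|---|---|---|
| 0.3 | sqrt(0.91 × 1.0097) = 0.96 | 1/0.9586 - 1 = 4% |
| 0.5 | sqrt(0.75 × 1.0097) = 0.87 | 1/0.8702 - 1 = 15% |
| 0.7 | sqrt(0.51 × 1.0097) = 0.72 | 1/0.7176 - 1 = 39% |

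For scale, with 63 per arm, two-sided 5% and 80% power, the detectable difference without the covariate is (1.960 + 0.842) × sqrt(2/63) = 0.499 SD. Multiplying by the ratios gives about 0.48, 0.43 and 0.36 SD. A chance pre-dose imbalance of 0.2 SD would shift the unadjusted estimate by rho × 0.2 = 0.06, 0.10 or 0.14 SD.

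**3. MAP off positive pressure**

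The SAP does write rules for comparable cases. Low-flow cannula is not positive pressure for BPD grading (6.1.4.8) and counts as oxygen alone for durations (6.1.4.10). Biomarkers outside the quantification limits are imputed (6.3.12.1.11). RSS and OSI have no such rule. Under SAP 6.3.4 a blank MAP stays blank.

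- The by-day model has one record per baby and day, so the baby leaves the Day 2 comparison.
- The 24-hour repeated-measures model keeps the baby's other time points. Under missing-at-random it does not estimate a comparison restricted to babies with a MAP.

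That the rule can matter is easily shown with invented values. Give every baby on pressure an RSS of 8 × 0.30 = 2.4, with 20% off pressure in one arm and 10% in the other. Blank gives a difference of 2.4 - 2.4 = 0. Zero gives 0.8 × 2.4 - 0.9 × 2.4 = -0.24. With 10% off in both arms, both rules give 0. At 30% against 10% the results are 0 and -0.48. The spread comes wholly from the assumed shares, so no size is claimed.

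**The case against.** **The mismatch is a wording slip.** Each SAP section names the code to be run, and that code has the covariate. This stands: nothing is lost if it is run. A reader might infer that the Day 2 analysis will be unadjusted and imprecise, but the documents do not show that. They show an ambiguity whose cost arises only if the text is preferred to the code.

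**A MAP default exists.** No imputation implies a blank, critical cases go to blind review, and the SAP sends details of respiratory support to a Data Review Report that is not available here and may hold a rule. This also stands. Nothing in the documents suggests that zero would be entered.

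**Size of the MAP effect.** A reader might infer that the Day 2 difference is materially biased toward no effect. That needs a rate of babies off pressure, a link between coming off and severity, and a notional RSS for babies who have no MAP. The documents supply none of these.

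**Scope.** A reader might also infer that all RSS and OSI results are conditional on having a MAP. That fits the Day 2 model only, not the 24-hour model.

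**The covariate may cost more than one degree of freedom.** The dosing modes in protocol 6.2.3 include babies on nCPAP. If pre-dose MAP is not recorded for them, they drop out of the adjusted model. This is a fair condition on the fix.

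**Conclusion.** The point holds as an inconsistency between text and code. The Day 2 RSS and OSI sentences in the protocol and SAP describe a model without the pre-dose value, and the code the SAP says it will use describes a model with it. Following the text would inflate the standard error by about 4% to 39% for assumed correlations of 0.3 to 0.7, with about 20 sites and all 126 babies contributing. Following the code loses nothing.

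The missing MAP rule is a secondary gap in detail. Its default effect, leaving babies without a MAP out of the Day 2 comparison, follows from the plan. Its size does not.

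Severity is minor. The study is exploratory, the RSS and OSI outputs carry no Key First Results asterisk (SAP section 8), and FiO2, SpO2/FiO2, ventilation duration and the room-air outcomes do not depend on MAP.

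**What to change.** **Main change.** In SAP 6.3.12.1.3 and 6.3.12.1.4, end the Day 2 sentence with *and pre-dose RSS (OSI) as covariate*, matching the by-day code. The SAP wording is enough; the protocol text can be noted as clarified by it. The cost is two clauses and one degree of freedom, using data already collected, provided pre-dose MAP is recorded for babies on nCPAP. The blind review should confirm that, because a baby without it would be lost from the adjusted model.

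**Secondary change.** Before unblinding, state in the same two sections how MAP is handled off positive pressure, or cite the Data Review Report if it already says. Report by arm and time point how many babies have no MAP and why (off pressure, death, not recorded). The number observed is already part of the descriptive statistics (SAP 6.3.1), so this adds one column of reasons per score. Label the Day 2 result, and only that result, as conditional on having a MAP.
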